	Is the FDA committed to protecting the public from possible risks of tobacco products?			Cred7_Post1	
	Do you believe that if the FDA knew that certain tobacco products are less harmful than thought, they would tell the public?			Cred8_Post1	
Page Break					
Mental Health ²⁰	During the past 30 days, about how often did you feel...	(question in matrix format)	MH1	MH1	MH1
	nervous?	4=All of the time	MH1_a_Pre	MH1_a_Post1	MH1_a_Post2
	hopeless?	3=Most of the time	MH1_b_Pre	MH1_b_Post1	MH1_b_Post2
	restless or fidgety?	2=Some of the time	MH1_c_Pre	MH1_c_Post1	MH1_c_Post2
	so depressed that nothing could cheer you up?	1=A little of the time 0=None of the time	MH1_d_Pre	MH1_d_Post1	MH1_d_Post2

Construct (Source)	Question Text	Response Option	Pretest Var Name	Post 1 Var Name	Post 2 Var Name
	that everything was an effort?		MH1_e_Pre	MH1_e_Post1	MH1_e_Post2
	worthless?		MH1_f_Pre	MH1_f_Post1	MH1_f_Post2
Page Break					
Instruction	Please select the bubble to answer the questions about the messages that you saw during the study:			AE_Inst_Post1	AE_Inst_Post2
Action expectancies ²¹	After seeing the messages, how likely are you to seek information about chemicals in cigarettes?	4=Very Likely 3=Likely 2=Unlikely 1=Very Unlikely		AE1_Post1	AE1_Post2
	After seeing the messages, how likely are you to seek help to quit smoking?	4=Very Likely 3=Likely 2=Unlikely 1=Very Unlikely		AE2_Post1	AE2_Post2
Page Break					
Instruction	Please select the bubble to show how much you agree or disagree with the statements below about the messages that you saw during the study:			React	
Reactance ²²	The messages were trying to manipulate me	5=Strongly agree 4=Somewhat agree 3=Neither agree nor disagree 2=Somewhat disagree 1=Strongly disagree		React_1_Post1	
	The messages made me feel aggravated			React_2_Post1	
	The health effects on the messages were overblown			React_3_Post1	
Page Break					
Conversations ^{23,24}	During the study, did you talk to others about the messages you received about cigarettes?	1=yes 0=no		Convo1_Post1	

Construct (Source)	Question Text	Response Option	Pretest Var Name	Post 1 Var Name	Post 2 Var Name
Page Break					
Conversation 5 ²⁴	[only display if convo1_Post1 = 1] When you talked about the messages, would you say your conversations were mostly...	1=Negative about smoking cigarettes 2=Neutral about smoking cigarettes 3=Positive about smoking cigarettes		Convo2_Post1	
Page Break					
Behavior Instructions	Please think about yesterday		Behav_Inst	Behav_Inst	Behav_Inst
	What time did you wake up yesterday?	Time	Time#1_Wake_Hour Time#1_Sleep_Hour Time#2_Wake_Min Time#2_Sleep_Min Time#3_Wake_AMPM Time#3_Sleep_AMPM		
	What time did you go to sleep last night?	Time			
Behavior ⁴	How many times yesterday did you dispose of your cigarette butts by dropping them on the ground?	Dropdown list 0-100, 101=refused	Lit1	Lit1	Lit1
	How many times yesterday did you dispose of your cigarette butts by throwing them or dropping them out of the car window?		Lit2	Lit2	Lit2
	How many times yesterday did you stop yourself from having a cigarette because you wanted to smoke less?		Forgo	Forgo	Forgo
	How many times yesterday did you butt out a cigarette before you finished because you wanted to smoke less?		Butt	Butt	Butt
PAGE BREAK					
Cigarettes Smoked ⁷	Yesterday, from the time you woke up until noon, how many cigarettes did you smoke?	Dropdown list 0-100, 101=refused	Cigs_Morn	Cigs_Morn	Cigs_Morn

Construct (Source)	Question Text	Response Option	Pretest Var Name	Post 1 Var Name	Post 2 Var Name
	Yesterday, from noon until you went to sleep, how many cigarettes did you smoke?		Cigs_Afternoon	Cigs_Afternoon	Cigs_Afternoon
PAGE BREAK					
Thinking Instructions ⁴	Overall yesterday, how much did you...		Think	Think	Think
Thinking About Chemicals ⁴	Think about the chemicals in the smoke from your cigarettes?	5=All of the time 4=Often 3=Sometimes 2=Rarely 1=Never	Think_Chem	Think_Chem	Think_Chem
Thinking About Risks	Think about the harm your smoking might be doing to you?		Think_Risk	Think_Risk	Think_Risk
Thinking About Littering	Think about discarding cigarette butts properly?		Think_Lit	Think_Lit	Think_Lit
Thinking about quitting	Think about quitting smoking?		Think_Quit	Think_Quit	Think_Quit
PAGE BREAK					
StudyInfo1	The next few pages give you some more information for what to expect during the study.		StudyInfo1		
PAGE BREAK			PAGE BREAK		
StudyInfo2	Starting tomorrow, you will receive an email at 7am every morning for 15 days from [contact]', with a link to a short survey. You have until 11am to open the link and answer the survey, or you will have to wait until the next one is sent. 		StudyInfo2		
PAGE BREAK			PAGE BREAK		

Construct (Source)	Question Text	Response Option	Pretest Var Name	Post 1 Var Name	Post 2 Var Name
StudyInfo4	
After 15 days (16 days from now), you will receive another email at 7am with a link to a 20-minute survey. You will have 24 hours to open the link and answer the survey.
 
Finally, you will receive another email 32 days from now with a link to a 20-minute survey. You will have 24 hours to open the link and answer the survey.
		StudyInfo4		
PAGE BREAK			PAGE BREAK		
StudyInfo5	
You will be paid for the study based on how many surveys you complete with a check that will arrive in the mail after you complete the study.
 
You will receive \$20 for completing this survey.
 
For the daily morning surveys, you will be paid \$4 for each survey that you complete.
 
For the 20-minute surveys at the end of the study, you will receive \$20 each if you complete them.
 
When data collection for the full study is complete, we will have a drawing for three Amazon gift cards, with a \$200 value. Entries into the drawing will be based on completion of the morning surveys.
 
Bonus system for Morning Survey Completion:
 
 • Bronze: Total of \$10 bonus for at least 9 morning surveys. 1 entry into Amazon gift card drawing. 		StudyInfo5		

Construct (Source)	Question Text	Response Option	Pretest Var Name	Post 1 Var Name	Post 2 Var Name
	
 Silver: Total of \$20 bonus for at least for at least 12 morning surveys. 2 entries into Amazon gift card drawing. Gold: Total of \$30 bonus for completing all 15 morning surveys. 3 entries into Amazon gift card drawing. 
If you complete all the surveys for this study, your check amount will be \$150.
				
PAGE BREAK					
Quality Assurance	When you took the surveys, ere you able to see each message?	0=No 1=Yes		QA1	
PAGE BREAK					
Quality Assurance	[IF QA1 = No] Why weren't you able to see each message, when you took the surveys?	[text box]		QA1_comment	
PAGE BREAK					
Quality Assurance	Were you able to read the text on each of the messages?	0=No 1=Yes		QA2	
PAGE BREAK					
Quality Assurance	[IF QA2 = No] Why weren't you able to read the text on each of the messages?	[text box]		QA2_comment	
PAGE BREAK					
Quality Assurance	Did you understand all of the questions?	0=No 1=Yes		QA3	
PAGE BREAK					
Quality Assurance	[IF QA3 = No] Which questions did you have trouble understanding and why?	[text box]		QA3_comment	
PAGE BREAK					
Quality Assurance	Would you do this study again?	0=No 1=Yes		QA4	

Construct (Source)	Question Text	Response Option	Pretest Var Name	Post 1 Var Name	Post 2 Var Name
Quality Assurance	Would you recommend this study to a friend?	0=No 1=Yes		QA5	
Quality Assurance	Did anything annoy you, if so, what?	[text box]		QA6	
Quality Assurance	Is there anything that you would like to share about your experience in the study?	[text box]		QA7	
Quality Assurance	Did you have any difficulty remembering how many cigarettes you smoked? If yes, please explain.	[text box]		QA8	
Quality Assurance	Would you have preferred to receive the surveys for this study via text message?	0=No 1=Yes		QA9	
PAGE BREAK					
Instructions for Enrolling in Survey Signal	
On the next page, you will be redirected to a new link (SurveySignal). It is very important that you fill out the information on that page (including name, email address, etc.). If you do not fill out that information, you will NOT be enrolled in the study. If you have any questions, email [contact].
 
Once you fill in your information, SurveySignal will send you an email to verify your email address. Please make sure that you verify your email, so that you will be enrolled in the study.
 
Note: If you are using a Mac, you will need to open the link in Chrome or Firefox.
		SurveySignal_Inst		
End of Survey for anyone that is no longer a	Unfortunately you are no longer eligible for our study. We will send you a check for \$20 to compensate you for your time completing this survey, but you will not be able to complete the rest of the study.				

Construct (Source)	Question Text	Response Option	Pretest Var Name	Post 1 Var Name	Post 2 Var Name
smoker (smoke_stat_ pre =0)	Thank you for taking the time to complete this survey!				

Morning Questionnaire (to be answered between 7am – 11am every morning)

Construct (Source)	Question Text	Response Option	Var Name
Study ID	[Auto-recorded]	numerical	
Behavior Instructions	Please think about yesterday		Behav_Inst
	What time did you wake up yesterday?	Time	Time#1_Wake_Hour
	What time did you go to sleep last night?	Time	Time#1_Sleep_Hour Time#2_Wake_Min Time#2_Sleep_Min Time#3_Wake_AMPM Time#3_Sleep_AMPM
Behavior ⁴	How many times yesterday did you dispose of your cigarette butts by dropping them on the ground?	Dropdown list 0-100, 101=refused	Lit1
	How many times yesterday did you dispose of your cigarette butts by throwing them or dropping them out of the car window?		Lit2
	How many times yesterday did you stop yourself from having a cigarette because you wanted to smoke less?		Forgo
	How many times yesterday did you butt out a cigarette before you finished because you wanted to smoke less?		Butt
PAGE BREAK			
Cigarettes Smoked ⁷	Yesterday, from the time you woke up until noon, how many cigarettes did you smoke?	Dropdown list 0-100, 101=refused	Cigs_Morn
	Yesterday, from noon until you went to sleep, how many cigarettes did you smoke?		Cigs_Afternoon
PAGE BREAK			
Thinking Instructions ⁴	Overall yesterday, how much did you...		Think
Thinking About Chemicals ⁴	Think about the chemicals in the smoke from your cigarettes?	5=All of the time 4=Often 3=Sometimes 2=Rarely 1=Never	Think_Chem
Thinking About Risks	Think about the harm your smoking might be doing to you?		Think_Risk
Thinking About Littering	Think about discarding cigarette butts properly?		Think_Lit
Thinking about quitting	Think about quitting smoking?		Think_Quit

Construct (Source)	Question Text	Response Option	Var Name
PAGE BREAK			
Instruction	Please view the message on the next screen. After 10 seconds, you will be able to click the '>>' to move forward to the next page. [Messages should appear at the top of the screen for all subsequent questions]		Morn_Inst1
Page Break			
Message	Condition 1 or 2(Arsenic, Formaldehyde, Uranium, Ammonia, Lead) Or Control Messages [This should appear on the screen for 10 seconds before participants are able to move on to questions on the next page]		Message
Page Break			
Affect Instruction	How much did the message make you feel...		Affect_Inst
Affect ²⁵⁻²⁷	Anxious?	5=Extremely 4=Very 3=Somewhat 2=A little 1=Not at all	Affect_1
	Sad?		Affect_2
	Scared?		Affect_3
	Guilty?		Affect_4
	Disgusted?		Affect_5
Page Break			
Credibility ²⁸	Please indicate how much you think the message is...		Cred_Inst
	Accurate	7 = Very accurate 1 = Not very accurate	Cred_1
	Authentic	7 = Very authentic 1 = Not very authentic	Cred_2
	Believable	7 = Very believable 1 = Not very believable	Cred_3
Page Break			

Construct (Source)	Question Text	Response Option	Var Name
Instruction	Please select the bubble to show how much you agree or disagree with the statements below:		PE_Inst
Perceived Effectiveness ²⁹	The message makes me concerned about the health effects of smoking.	5=Strongly agree	PE_1
	The message makes smoking seem unpleasant to me.	4=Somewhat agree	PE_2

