Gay, lesbian, or bisexual								
Current Cigarette Smoking								
Current smoker								
Nonsmoker								
Fagerstrom Nicotine Dependence Score (FTND)								
Trust in FDA								
Number of Times Participants Viewed a Message During Follow Up								

To update Table 1 see 'Table 1 V1.xlsx' in Analysis Plan folder

Analysis

Outcome definitions

- Quit intentions [Time Frame: day 16] PRIMARY OUTCOME
 - 3 item measure with high reliability, average of the 3 items to create a score range 1-4 (Brewer et al., 2016, 2018; Klein, Zajac, & Monin, 2009)
 - We will compare the differences between pre and post
- Number of cigarettes smoked each day [Time Frame: Measured daily on days 1-15]
 - Continuous, Modified from FTND (Heatherton, Kozlowski, Frecker, & Fagerström, 1991; Storr, Reboussin, & Anthony, 2005)
- Number of cigarettes forgone each day [Time Frame: Measured daily on days 1-15]
 - Continuous, adapted from Brewer 2016 (Brewer et al., 2016)
 - May be zero inflated, if yes, may choose to dichotomize to 0/1
- Number of cigarettes butted out each day [Time Frame: Measured daily on days 1-15]
 - Continuous, adapted from Brewer 2016 (Brewer et al., 2016)
 - May be zero inflated, if yes, may choose to dichotomize to 0/1
- Quit attempts during the study [Time Frame: Measured on days 16 and 32]
 - Adaptation from Fagan (Fagan et al., 2007)
 - May be zero inflated, if yes, may choose to dichotomize to 0/1
- Awareness of quitline [Time Frame: Measured on day 16]
- Recall of quitline phone number [Time Frame: Measured on day 16]
- Use of the quitline during the study [Time Frame: Measured on days 16 and 32]
- Intention to use the quitline [Time Frame: Measured on days 16 and 32]
- Quit intentions [Time Frame: Measured on day 32]
 - 3 item measure with high reliability, average of the 3 items to create a score range 1-4 (Brewer et al., 2016, 2018; Klein et al., 2009)
 - We will compare the differences between pre and post
- Self Efficacy [Time Frame: Measured on days 16 and 32]

- 1 item (“IARC HANDBOOKS OF CANCER PREVENTION,” n.d.; Thrasher, Swayampakala, Borland, et al., 2016; Thrasher, Swayampakala, Cummings, et al., 2016)
- Response Efficacy [Time Frame: Measured on days 16 and 32]
 - 1 item (Thrasher, Swayampakala, Cummings, et al., 2016)

Analysis Methods

Analysis methods will depend on the time point that the outcome was measured. Post test measures will be analyzed differently than measures from the daily surveys, as outlined below.

Post test measures

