What analysis method will be used and how treatment effects will be presented

Linear regression for continuous outcomes, logistic for dichotomous.

Any adjustment for covariates

Covariates included for the imputation (in addition to treatment group):

- Dose of ads (# of times participants viewed a message)
- Gender (Male, Female, Other) (The GenIUSS Group, 2014)
- Age (continuous)
- Poverty Status (Above or Below Poverty Line)(Brewer et al., 2018; Department of Health and Human Services, 2017)
- Education (6 categories, same as phone survey)
- FTND Sum Using scoring from Heatherton et al. 1991 (Fagerstrom Test for Nicotine Dependence)(Fagerstrom, Heatherton, & Kozlowski, 1990; Heatherton et al., 1991)

Covariates included in the analysis model (in addition to treatment group):

- Dose of ads (# of times participants viewed a message)

Methods used for assumptions to be checked for statistical methods

For continuous outcomes, we assume the distribution of dependent variable given a predictor variable (intervention) is 1) independent 2) normality 3) constant variance (homogeneity of variance). We can check normality with Q-Q plot of the residual or perform Wilk-Shapiro test and use a scatter plot of residual on predictor variable (intervention) to check independence and constant variance.

Details of alternative methods to be used if distributional assumptions do not hold (eg normality, proportional hazards, etc)

If we have a violation for normality assumption, we can have two options: 1) transform our data so that the shape of our response variable become normally distributed or 2) choose the non-parametric method like Kruskal-Wallis which does not require the assumption of normality. The ANOVA can be considered a robust test against the normality assumption though. If the assumption of homogeneity of variances has been violated, we can use Welch or Brown and Forsythe test. Even though we alternatively perform a Kruskal-Wallis test, in most cases, Welch test is best. We don't expect to have dependency issues in our data.

Any planned sensitivity analyses for each outcome where applicable

Sensitivity analyses may be carried out using a 'complete case analysis' framework

Any planned subgroup analyses for each outcome including how subgroups are defined

None a priori

Missing Data

Multiple imputation will be used so that everyone who was randomized to an intervention will be included in the primary analysis

Additional Analyses

None a priori

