Nicotine Dependence ⁷	How many cigarettes per day do you smoke?	0 = 10 or less 1 = 11-20 2 = 21-30 3 = 31 or more	FTND4_Pre	FTND4_Post1	FTND4_Post2
	Do you smoke more frequently during the first hours after waking than during the rest of the day?	1 = Yes 0 = No	FTND5_Pre	FTND5_Post1	FTND5_Post2
	Do you smoke if you are so ill that you are in bed most of the day?	1 = Yes 0 = No	FTND6_Pre	FTND6_Post1	FTND6_Post2
Page Break					
Previous Quit Attempts ⁸	How many times during the past 12 months have you stopped smoking for 1 day or longer because you were trying to quit smoking?	Dropdown (0-365)	PQA_Pre		
Quit Attempts ⁸	Since you started this study, how many times have you stopped smoking for 1 day or longer because you were trying to quit smoking?			QuitAtt_Post1 Dropdown 0-16	QuitAtt_Post2 Dropdown 0-32
Smoking Status ⁹	Do you now smoke cigarettes every day, some days or not at all?	2=Every day 1=Some days 0=Not at all	Smoke_Stat_Pre	Smoke_stat_pos t1	Smoke_Stat_post 2
Page Break					

Construct (Source)	Question Text	Response Option	Pretest Var Name	Post 1 Var Name	Post 2 Var Name
Quit Line Awareness	Do you know what national phone number you can call for help to quit smoking?	1 = Yes 0 = No (If no, skip the next question)		QLAware1	
Page Break					
Quit Line Awareness follow up	What is the national phone number?	Text Box		QLAware2	
Page Break					
Quitline Use	Since you started this study, have you called the Quitline (national phone number for help to quit smoking)?	1 = Yes 0 = No		QL_Use_Post1	QL_Use_Post2
Page Break					
Quit Intention ^{4,10}	How interested are you in quitting smoking in the next month?	4=Very interested 3=Somewhat interested 2=A little interested 1=Not at all interested	QI1_Pre	QI1_Post1	QI1_Post2
	How much do you plan to quit smoking in the next month?	4=Very much 3=Somewhat 2=A little 1=Not at all	QI2_Pre	QI2_Post1	QI2_Post2
	How likely are you to quit smoking in the next month?	4=Very likely 3=Somewhat likely 2=A little likely 1=Not at all likely	QI3_Pre	QI3_Post1	QI3_Post2
PAGE BREAK					
Quitline Intention	If you were to quit smoking in the next month, how likely are you to call the national quitline for help?		QLI_Pre	QLI_Post1	QLI_Post2
Littering Intention ⁴	How likely are you to dispose of your cigarette butts by dropping them on the ground in the next month?		LI_Pre	LI_Post1	LI_Post2
Page Break					

Construct (Source)	Question Text	Response Option	Pretest Var Name	Post 1 Var Name	Post 2 Var Name

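### The quit-attempt comparisons at days 16 and 32 leave out the pre-randomisation count of past-year quit attempts, a minor and free gain in power that may be near zero or worth up to about 8 to 9 points

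*Combined protocol and SAP*

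**What the plan says.** **The outcome.** The SAP's Outcome definitions list "Quit attempts during the study [Time Frame: Measured on days 16 and 32". The outcome is not primary; quit intentions at day 16 are. On its form the SAP says "May be zero inflated, if yes, may choose to dichotomize to 0/1".

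**The items.** In Appendix A (Pre, Post 1, Post 2) the post-test item is "Since you started this study, how many times have you stopped smoking for 1 day or longer because you were trying to quit smoking", with a dropdown of 0-16 at post-test 1 and 0-32 at post-test 2. The pre-test item, PQA_Pre, is "How many times during the past 12 months have you stopped smoking for 1 day or longer because you were trying to quit smoking", with a dropdown of 0-365. The Randomization section places assignment at the end of the baseline survey, so PQA_Pre is answered before allocation.

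**The model.** For post-test measures the method is "Linear regression for continuous outcomes, logistic for dichotomous". Under "Covariates included in the analysis model (in addition to treatment group" there is one entry: "Dose of ads (# of times participants viewed a message". Under "Covariates included for the imputation (in addition to treatment group" the SAP lists dose, gender, age, poverty status, education and the FTND sum. PQA_Pre is in neither list, nor in Draft Table 1. The SAP's statement that pre and post will be compared is attached only to quit intentions.

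**Missing data.** The Analysis Populations section allows secondary outcomes to be analysed on complete cases without imputation.

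**The concern.** The trial collects, before allocation, a count of exactly the event that it later uses as an outcome, and the SAP does nothing with it. Smokers who have tried to quit several times in the past year may well differ from those who have not in how often they try during the study. If so, that difference stays in the unexplained variation of each arm comparison, although a variable that could remove part of it is already in the dataset.

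The stake is efficiency on a non-primary outcome. The sample size was set for quit intention, and no power is stated for quit attempts, so any precision available at no cost is useful there. If this outcome is imputed, leaving PQA_Pre out also drops a plausible predictor of the missing values.

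A fix that gave each outcome its own baseline value would not reach this item. Quit attempts since study start have no baseline value, and PQA_Pre is a separate variable that has to be named.

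**Working it through.** **1. Inputs from the documents.** Event definition, recall windows and dropdown ranges: Appendix A. Model and covariate lists: SAP, Post test measures. Alpha 0.05: Statistical Principles. Sizing of 253 per group for d = 0.25 and 80% power, and the recommended total of 800: Sample Size. With equal allocation, 800/3 = 266.7, so 266 or 267 per arm.

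**2. Inputs that must be assumed.** The proportion making any attempt, the arm difference, and the correlation between past-year and in-study attempts. The documents give none of these.

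**3. The plan's own figure.** For a two-sided t-test, n = 2(1.96 + 0.842)²/0.25² = 251.2, so 252 per arm. The exact t solution is 252.13, so 253, and 3 × 253 = 759. The stated figures reproduce. They concern quit intention; no figure is stated for quit attempts.

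**4. If the count is kept and analysed by linear regression.** Adjusting for a covariate with correlation ρ multiplies the residual variance by 1 − ρ². Taking d = 0.25 purely as an illustration, power = Φ(0.25/[√(1 − ρ²)·√(2/266)] − 1.96):

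| ρ | 1 − ρ² | Power, 266 per arm | Gain (points) |
|---|---|---|---|
| 0 | 1.00 | 82.2% | – |
| 0.1 | 0.99 | 82.6% | 0.4 |
| 0.2 | 0.96 | 83.7% | 1.5 |
| 0.3 | 0.91 | 85.6% | 3.4 |
| 0.4 | 0.84 | 88.2% | 6.0 |
| 0.5 | 0.75 | 91.5% | 9.3 |

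**5. If the outcome is dichotomised and analysed by logistic regression.** Simulation with 267 per arm, any attempt in 20% against 30%, Wald test of the arm effect, 2,000 runs per setting, standard normal predictor, dose not modelled:

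| Correlation with any attempt | Unadjusted | Adjusted | Gain (points) |
|---|---|---|---|
| 0.16 | 76.7% | 77.8% | 1.1 |
| 0.27 | 75.6% | 78.8% | 3.2 |
| 0.36 | 75.9% | 81.8% | 5.9 |
| 0.45 | 77.0% | 86.4% | 9.4 |

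The simulation error of each power estimate is about √(0.77 × 0.23/2000) = 0.009, or 0.9 points.

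A normal predictor is not a count, so the check was repeated with a skewed log-count predictor at the same rates and arm size. There was no gain at correlations up to about 0.17, about 4 points at 0.30 and about 8 points at 0.41.

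**6. A second count-based check.** Past-year and in-study counts were simulated as Poisson with a shared gamma-distributed personal rate (266 per arm, 1,500 runs, rate ratio 1.6, log-transformed baseline count). At a raw count correlation of about 0.37, logistic power rose from 63.7% to 70.7%. At about 0.61 it rose from 53.5% to 69.2%. This design assumes that one stable personal rate drives both counts, which favours the covariate, and the second setting lies beyond the correlations used for the conclusion.

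**7. Validity.** With no arm effect in the same simulation, rejection was 4.5% (linear) and 4.6% (logistic) without the covariate, and 4.1% in both with the log count.

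**The case against.** The strongest reply is that this is a preference about efficiency and that the plan contains no error here. That is right as far as it goes. Omitting a prognostic covariate from a randomised comparison is valid, no stated figure is wrong, and the outcome is one of many non-primary ones that the trial was not sized for.

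The second reply is that the size rests on assumption. This stands too. Nothing in the documents shows that past-year attempts predict attempts over 16 or 32 days, and at a correlation of about 0.08 a rerun gave 76.6% against 76.9%, effectively no gain. The simulations also leave out the SAP's dose covariate.

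The third reply is that adjustment changes the target if the outcome is dichotomised. Logistic adjustment raises power for a conditional odds ratio; it does not shrink the standard error as it does in a linear model. This is a reporting matter and no reason to leave the covariate out.

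Three stronger readings are tempting, and the documents do not support them:
- A reader might take PQA_Pre for the baseline value of the outcome. The event definition is the same, but the window is 12 months in one item and the time since study start in the other. It is a prognostic covariate, and no change score can be formed.
- A reader might infer that the trial's only post-test measure of quitting-related behaviour is affected. Use of the quitline is also a listed outcome at days 16 and 32.
- A reader might infer that the imputation is deficient for this outcome. The SAP lets secondary outcomes skip imputation, so this applies only if quit attempts are imputed.

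**Conclusion.** The point holds as a minor, free improvement. The SAP leaves a relevant pre-randomisation item out of the quit-attempt models at days 16 and 32, and out of the imputation model. The comparison stays unbiased and type I error is not inflated; a reader should not infer otherwise.

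What may be lost is power: about 0 points if the correlation is 0.2 or less, and about 8 to 9 points at 0.40 to 0.45. That range assumes 267 per arm, any attempt in 20% against 30%, and logistic regression. The linear calculation gives gains of similar size. The direction is secure if past attempts predict new ones. The documents do not settle the size, and it may be negligible.

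**What to change.** In the SAP, Post test measures, adjustment for covariates:
- Add log(1+PQA_Pre) as a pre-specified covariate in the quit-attempt models at day 16 and day 32.
- Add the same term to the imputation model if quit attempts are imputed.
- If the outcome is dichotomised, label the result as an adjusted (conditional) odds ratio.

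One coding should be fixed in advance so that no analyst choice is added to an outcome whose dichotomisation is already open. The log form is suggested because the dropdown runs to 365, where a few large raw values could dominate; on the log scale the range is 0 to ln(366) = 5.9. Little hangs on the choice: in the simulated counts with correlation 0.37, log and raw coding gave 70.7% and 70.3% power in the logistic model, and 83.8% and 84.9% in the linear one.

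The cost is one line in the SAP and one term in the SAS code. The item is already collected. The only downside is the conditional interpretation of the odds ratio.

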- Adherence for the daily surveys will be presented with completion % as well as the mean number complete by treatment group
- Completion of post test surveys will be presented by % completing each by treatment group

Definition of protocol deviations for the trial

- Minor protocol deviation: change in eligibility (ex: turning 66) between screening and baseline
- Minor protocol deviation: completing the wrong sequence of message days due to survey signal error
- Major protocol deviation: No protocol deviations in this trial will impact the safety or physical or mental integrity of the participants in the trial. A slightly older participant, or a participant that receives a slightly different number of messages will both be included as covariates during analysis, so they will not impact the scientific validity of the trial. Therefore, we do not classify any protocol deviations as 'major'

Description of which protocol deviations will be summarized

- Protocol deviations will not be summarized overall, but data related to the deviations will be included in manuscripts. For example, we will not say X participants were older than 65, but will include mean age in a demographic table by treatment group. Similarly, we will not include how many people completed an extra 'day' of the protocol, but we will report the mean number of days participants completed by treatment group.

Analysis Populations

Definition of analysis populations

Outcomes assessed only at post test (including quit intentions) will be analyzed using multiple imputation such that everyone who was randomized will be included in the analysis, and those with missing outcome data will have their outcomes imputed.

For outcomes that were measured daily, all participants that completed at least one of the daily surveys will be included in the planned repeated measure models.

Secondary outcomes may be analyzed using complete case analysis, without imputation.

Trial Population

Screening Data

Screening data will be provided based on the CONSORT guidelines, and CONSORT flow chart will be included with publications.

Eligibility

Minimum Age: 18 Years

Maximum Age: 65 Years

Sex: All

Gender Based: No

Inclusion Criteria:

[figure not shown]
- Have smoked at least 100 cigarettes in his or her lifetime
- Currently smoke cigarettes every day or some days
- Work or home access to the internet
- Email account that is regularly used
- Lives in the US
- Comfortable taking a survey in English

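### Day-32 quit attempts and quitline use are asked cumulatively, but the plan has no rule that keeps a day-16 event when the day-32 survey is missing

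*Combined protocol and SAP*

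**What the plan says.** The Appendix A item on quit attempts reads "Since you started this study, how many times have you stopped smoking for 1 day or longer because you were trying to quit smoking". It has one wording for both post-tests. The response list runs from 0 to 16 at the first and is "QuitAtt_Post2 Dropdown 0-32" at the second, so the later item covers the whole study and not only the days since the first. The quitline item, "Since you started this study, have you called the Quitline", is a yes/no question over the same window, also put at both post-tests.

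The SAP's Outcome definitions give each of these one entry: "Quit attempts during the study [Time Frame: Measured on days 16 and 32" and "Use of the quitline during the study [Time Frame: Measured on days 16 and 32". They do not say how the two surveys are combined. They do allow quit attempts to be reduced to yes/no.

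Two routes exist for a missing post-test. Analysis Populations provides for multiple imputation of post-test outcomes, but adds: "Secondary outcomes may be analyzed using complete case analysis, without imputation". Under Post test measures, the list headed "Covariates included for the imputation (in addition to treatment group" names dose of ads, gender, age, poverty status, education and FTND. The day-16 answer is not on it. No text carries a day-16 event forward or sets a floor for an imputed count.

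**The concern.** A participant who reports a quit attempt or a quitline call at day 16 has, by the wording of the question, a known yes at day 32 even if the second post-test is never returned. Both written routes can treat that result as unknown. Complete case removes the person. Imputation from the listed variables can give the person a no, or a count below the one already reported.

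This can readily happen. Withdrawal/follow-up has a category for losses between days 16 and 32, and each post-test closes 24 hours after it is sent. These two outcomes record quitting behaviour and help-seeking, so discarding recorded events costs precision. It also biases the day-32 rates if loss after day 16 is related to having made an attempt.

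**Working it through.** **Plan's own figures.** The documents give no event rate, loss rate or power for these outcomes. The only sample-size figure, 253 per group for d = 0.25 at 80% power, concerns the primary outcome. It reproduces (two-sided t-test, 252.13 rounded up to 253; 3 × 253 = 759), and nothing below depends on it. The per-arm number used here is 800/3 ≈ 267.

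**Assumptions (none are in the documents).** The outcome is yes/no. Day-16 attempts are p = 30% in one arm and 20% in the other. New attempts by day 32 among those with none at day 16 are q = 15%. Loss after day 16 is a among day-16 attempters and b among the others, the same in both arms.

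**Formulas**
- True day-32 rate: p + (1 − p)q
- Rate among day-32 responders: [p(1 − a) + (1 − p)(1 − b)q] / [p(1 − a) + (1 − p)(1 − b)]
- Known events lost per arm: 267 × p × a

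Imputation without the day-16 answer reproduces the responder rate in expectation, unless the listed variables happen to predict day-16 attempts.

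**True rates.** 0.30 + 0.70 × 0.15 = 40.5%; 0.20 + 0.80 × 0.15 = 32.0%; difference 8.5 points.

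**Second post-test used alone**
- a = b = 10%: 0.3645/0.90 = 40.5% and 0.288/0.90 = 32.0%; difference 8.5 points, no bias. Known events lost: 267 × 0.30 × 0.10 = 8.0 and 267 × 0.20 × 0.10 = 5.3.
- a = 20%, b = 10%: 0.3345/0.87 = 38.4% and 0.268/0.88 = 30.5%; difference 8.0. Events lost: 16 and 11.
- a = 30%, b = 10%: 0.3045/0.84 = 36.25% and 0.248/0.86 = 28.8%; difference 7.4. Events lost: 24 and 16.
- a = 5%, b = 10%: 0.3795/0.915 = 41.5% and 0.298/0.91 = 32.7%; difference 8.7.

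**Impossible values.** A lost day-16 attempter is imputed as no with probability 1 minus the responder rate. At a = b = 10% that is 59.5% and 68.0%, or 8.0 × 0.595 ≈ 4.8 and 5.3 × 0.68 ≈ 3.6 people per arm in each imputed data set. At a = 20% or 30% with b = 10%, the range is about 62% to 71%.

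**Scale.** The standard error of the true difference is √(0.405 × 0.595/267 + 0.32 × 0.68/267) ≈ 4.1 points. The shifts of 0.5 and 1.1 points are about 0.12 and 0.27 of that.

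**Quitline use.** With an assumed 2% positive at day 16 and 5% to 30% loss among them, 267 × 0.02 × 0.05 = 0.3 to 267 × 0.02 × 0.30 = 1.6 known events per arm are lost.

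**Carrying events forward within complete case.** If day-16 positives are kept and all other people without day-32 data are dropped, the rate is [p + (1 − p)(1 − b)q] / [p + (1 − p)(1 − b)].
- 10% loss: 0.3945/0.93 = 42.4% and 0.308/0.92 = 33.5%; difference 8.9.
- 20% loss: 0.384/0.86 = 44.7% and 0.296/0.84 = 35.2%; difference 9.4.

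Both exceed the true 8.5, although loss is unrelated to day-16 status and plain complete case would have been unbiased.

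**The case against.** The SAP does not state that the day-16 answer will be ignored. Each outcome has a single whole-study entry, whereas quit intentions has separate entries for day 16 and day 32, so the analysts may intend to use both surveys. The imputation list does not forbid further variables, and complete case is optional. All of this stands: the point is conditional on day 32 being analysed from the second post-test alone. But no derivation rule is written, and following the listed variables literally leads to the problem.

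A reader might also infer that the plan biases these comparisons towards no difference. The documents do not support that. They give no reason to expect attempters to leave more often; attempters could equally be the more engaged participants, and the shift then goes slightly the other way.

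A reader might infer a large effect. A true 9.0-point difference can fall to 4.5 (30% v 20% at day 16, 10% new attempts), but only if the extra loss, 30% of attempters against 10% of everyone else, occurs in one arm alone. Nothing in the documents points to that pattern.

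Finally, a carry-forward rule has risks of its own. It biases rates upward if combined with complete case, and it needs an answer for people whose second report is lower than their first. Both objections are right and shape the fix.

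**Conclusion.** The point holds as a gap in the derivation and missing-data rules for two secondary outcomes. The logical part needs no assumed rates: whenever a day-16 positive misses the second post-test, a result fixed by the question's wording can be dropped or contradicted. The day-16 primary outcome, its sample size and any day-16 analysis of these two outcomes are unaffected.

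The size rests wholly on assumption. If loss is unrelated to day-16 status, the cost is precision and impossible values, not bias. If loss is related to it in the same way in both arms, the bias in the scenarios examined is between −1.1 and +0.2 points, small beside sampling error and of uncertain sign. For quitline use the effect is at most one or two people per arm in the range tried. If attempts are kept as counts, the error is an imputed value below the day-16 count, which need not be zero. This is a worthwhile, inexpensive improvement, not a threat to the trial's conclusions.

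**What to change.** Amend Analysis Populations, Outcome definitions and the imputation text under Post test measures, for the day-32 (whole-study) versions of these two outcomes only:

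1. Count a positive day-16 answer as positive at day 32, and bound any imputed QuitAtt_Post2 below by QuitAtt_Post1.
2. Add the day-16 answer to the imputation model, and impute every other missing day-32 value.
3. Do not combine the carry-forward with complete case, whether in the main analysis or in the optional sensitivity analysis.
4. Apply the same ever-reported rule to people who completed both surveys, so that a second answer lower than the first is handled consistently.

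This needs a few SAP sentences and a derivation step on data already collected. The price is a little more programming and reliance on the day-16 self-report where the two answers conflict.
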